6.4.3.7 Disease progression

Disease progression can be considered as a worsening of a patient’s condition attributable to the disease for which the investigational product is being studied. It may be an increase in the severity of the disease under study and/or increases in the symptoms of the disease. Events, which are unequivocally due to disease progression, should not be reported as an AE during the study.

6.4.3.8 Follow-up of unresolved adverse events

Any AEs that are unresolved at the end of the study (Visit 9) or at discontinuation, will be followed up until resolution by the investigator or until the investigator decides that no further follow-up is necessary, but without further recording in the eCRF. AstraZeneca retains the right to request additional information for any patient with ongoing AEs/SAEs at the end of the study, if judged necessary. The requirement to follow-up is not intended to delay database lock or production of the CSR. Both these activities should proceed as planned with ongoing AEs if necessary.

Any follow-up of ongoing SAEs after database lock will be reported to AstraZeneca, who will notify the appropriate Bristol-Myers Squibb Pharmacovigilance contact.

6.4.3.9 Adverse events reported after the end of treatment

Only unsolicited SAEs will be collected for a period of up to 30 days after the last dose of investigational products. All SAEs and associated concomitant medication will be recorded and reported to AstraZeneca who will notify Bristol-Myers Squibb Pharmacovigilance, see Section 13.1.

6.4.3.10 Reporting of hypoglycaemic events

Hypoglycaemic events (see Section 6.4.11) should be reported in a separate ‘Hypoglycaemic AE’ section in the eCRF.

Hypoglycaemic events should not be recorded in the regular AE section, except if the hypoglycaemic event fulfils the definition for an SAE, when it should be reported in the ‘SAE’ section in the eCRF.

6.4.4 Reporting of serious adverse events

All SAEs have to be reported, whether or not considered causally related to the investigational product, or to the study procedure(s). All SAEs will be recorded in the eCRF.

If any SAE occurs in the course of the study, then investigators or other study centre personnel will inform appropriate AstraZeneca representatives within one day, i.e., immediately but **no later than the end of the next business day** of when he or she becomes aware of it.

The designated AstraZeneca representative works with the investigator to ensure that all the necessary information is provided to Bristol-Myers Squibb Global Pharmacovigilance & Epidemiology **within one calendar day** of initial receipt for all SAEs. The AstraZeneca representative will notify the appropriate Bristol-Myers Squibb Pharmacovigilance contact to ensure regulatory compliance.

For fatal or life-threatening AEs where important or relevant information is missing, active follow-up is undertaken immediately. Investigators or other study centre personnel will inform AstraZeneca representatives of any follow-up information on a previously reported SAE within one calendar day, i.e., immediately but **no later than the end of the next business day** of when he or she becomes aware of it.

The reference document for definition of expectedness is the Investigators Brochure for the investigational product and the European Union (EU) Summary of Product Characteristics (SPC) for the active comparator product.

6.4.4.1 Serious adverse event handling using Web Based Data Capture (WBDC)

Serious AE (SAE) information will be entered and submitted into the WBDC system on the relevant eCRF pages. An automated e-mail alert will be sent to the designated AstraZeneca representative who will work with the investigator to ensure that all the necessary information is available in the system within the required time frames. The AstraZeneca representative will send a completed SAE report to the appropriate Bristol-Myers Squibb Pharmacovigilance representative via fax or e-mail.

If the WBDC system is not available, then the investigator or other study centre personnel reports a SAE to the appropriate AstraZeneca representative by telephone. The AstraZeneca representative will advise the investigator/study centre personnel how to proceed.

A paper back-up SAE report should be sent to the AstraZeneca representative, who will notify Bristol-Myers Squibb, recognising that the same reporting time frames still apply. The investigator is responsible for completing the eCRF as soon as the system becomes available again.

6.4.5 Laboratory safety assessment

Blood and urine samples for determination of clinical chemistry, haematology and urinalysis tests will be taken at the times indicated in [Table 3](#). The date and time of sampling will be recorded on the laboratory requisition form. The samples will be processed by the central laboratory and results will be reported back to the study centre within 72 hours.

All samples should be taken by adequately trained study personnel, and performed and handled in accordance with given instructions in the Laboratory Manual. Up to date reference ranges will be provided during the study and laboratory results will be compared to the laboratory standard normal ranges and flagged if they are outside the normal range. The investigator should make an assessment of the available results with regard to clinically significant abnormalities. The laboratory reports should be signed and retained at the study centre as source data for laboratory variables.

For information on how AEs based on laboratory tests should be recorded and reported, see [Section 6.4.3](#).

The complete list of safety laboratory variables is displayed in [Table 3](#).

Table 3 Safety laboratory variables

Visit number	1	2	3	4	5	6	7	8	9
Study Week	-2	-1	1	4	8	12	16	20	24
Study Day	-14	-7	1	28	56	84	112	140	168
Haematology									
Haemoglobin		X	X			X			X
Haematocrit		X	X			X			X
Red blood cell count		X	X			X			X
White blood cell count and differential		X	X			X			X
Platelet count		X	X			X			X
Clinical chemistry									
Aspartate aminotransferase (AST)		X	X			X			X
Alanine aminotransferase (ALT)		X	X			X			X
Alkaline phosphatase		X	X			X			X
Creatine kinase (CK)		X	X			X			X
Total bilirubin		X	X			X			X
Total protein		X	X			X			X
Albumin		X	X			X			X
Blood urea nitrogen (BUN)		X	X			X			X
Electrolytes:		X	X			X			X
- Sodium									
- Potassium									
- Chloride									
Serum creatinine (SCr) for estimation CrCl (Cockcroft Gault)		X	X			X			X

Visit number	1	2	3	4	5	6	7	8	9
Study Week	-2	-1	1	4	8	12	16	20	24
Study Day	-14	-7	1	28	56	84	112	140	168
Thyroid stimulating hormone (TSH) ^a			X						
Follicle stimulating hormone (FSH) ^b			X						
Total Cholesterol									X
HDL-C			X						X
LDL-C			X						X
TG			X						X
Urinalyses									
pH		X	X			X			X
Protein ^c		X	X			X			X
Glucose		X	X			X			X
Leukocyte esterase ^c		X	X			X			X
Blood by dipstick ^c		X	X			X			X
Pregnancy test ^d		X	X	X	X	X	X	X	X
Albumin:creatinine ratio		X	X			X			X

a. If abnormal, refer to free levothyroxine (T₄).

b. For women on hormone replacement therapy.

c. Microscopy if dipstick positive for blood, leukocyte esterase or protein.

d. Urine beta human chorionic gonadotropin (hCG) pregnancy test for women of childbearing potential (hCG minimum sensitivity of 25 IU/L) (dipstick analysed at the study centre).

For blood volume collected, see Section 7.1

6.4.6 Physical examination

A physical examination will be performed according to common medical practice at Visit 2 and Visit 9. The physical examination includes an evaluation of general appearance, lymph nodes, thyroid, musculoskeletal system, extremities, cardiovascular system, lungs, abdomen, reflexes and measurement of vital signs. Baseline data is collected at Visit 3, and findings are entered into the eCRF. New findings at the physical examination at Visit 9 are recorded as a change from Baseline.

A brief physical examination will be performed from Visit 3 to Visit 8 and includes an evaluation of general appearance, extremities, cardiovascular system, lungs, abdomen and measurement of vital signs to verify the findings from the physical examination at Baseline (Visit 3).

Any changes since Visit 1 will be recorded as AEs if the change is considered clinically significant by the investigator. For more information on how AEs based on examinations and tests should be recorded and reported, see Section 6.4.3.

6.4.7 ECG

A 12-lead ECG will be taken (supine position, standard ECG with a paper speed of 50 mm/second covering at least 6 sequential beats) after the patient has been lying down resting for at least 5 minutes at Visit 3 and Visit 9. The 12-lead ECG will be evaluated by the investigator and assessed as 'Normal' or 'Abnormal clinically significant' or 'Abnormal not clinically significant' in the eCRF.

For information on how AEs based on examinations and tests should be recorded and reported, see Section 6.4.3.

6.4.8 Vital signs

Vital signs will be assessed at all scheduled visits from Visit 2 to Visit 9 following the Study Plan provided in Section 3.1.

6.4.8.1 Blood pressure and pulse rate

Blood pressure and pulse rate will be measured using a standardised cuff adapted to the size of the patient's arm after the patient has been sitting and resting for at least 5 minutes and before blood samples are taken.

6.4.9 Weight and height

The patient's weight will be recorded in kilogram (kg), on a fasting stomach with light clothing and no shoes at Visit 2 and all scheduled visits from Visit 3 to Visit 9. The patient's height will be recorded in centimetres, without shoes, at Visit 2.

6.4.10 Waist circumference

The waist circumference will be measured in the morning at Visit 3 and again at Visit 9, before breakfast in a standing position at the natural waist (smallest waist circumference). If there is no natural waist, the measurement should be made at the level of the umbilicus.

6.4.11 Hypoglycaemic events

The patient will be asked to self-monitor plasma glucose levels and symptoms suggestive of hypoglycaemia and to register if a finger stick value was obtained and the glucose value in the supplied patient diary.

A hypoglycaemic event can be either:

- An episode with symptoms and confirmed low glucose
- An episode with low glucose
- An episode with symptoms when glucose was not measured

For the evaluation of hypoglycaemic events, special attention will be given to hypoglycaemia as defined in accordance with the CPMP guidance on clinical investigation of medicinal products in the treatment of diabetes mellitus (CPMP 2002), as described below:

- Major hypoglycaemic events, defined as symptomatic events requiring external assistance due to severe impairment in consciousness or behaviour, with plasma glucose level <3.0 mmol/L (<54 mg/dL), and prompt recovery after glucose or glucagon administration.
- Minor hypoglycaemic event, defined as either a symptomatic event with plasma glucose level <3.0 mmol/L (<54 mg/dL), and no need for external assistance, or an asymptomatic blood glucose measurement <3.0 mmol/L (<54 mg/dL).
- Events suggestive for hypoglycaemia, with symptoms that the patient experiences as hypoglycaemia and no confirmative measurement.

Plasma glucose values will be obtained from the central laboratory. Therefore, the corresponding plasma glucose values will be used to define hypoglycaemia, that is, plasma glucose <3.0 mmol/L (<54 mg/dL).

Data to be collected for each hypoglycaemic event:

- Date of start and stop and time of the day for start
- If symptoms are present or not and which symptoms
- If finger-stick value obtained and the plasma glucose value

- Intervention needed for recovery, maximum intensity, action taken, causality and possible contributing factors

The patient diary will be reviewed and data regarding hypoglycaemic events transcribed into the eCRFs at each scheduled visit. A new diary for the next visit period will be handed over to the patient. If a major hypoglycaemic event occurs, or more than one minor event since the last visit, the patient should contact the investigator. For the reporting of hypoglycaemic events/symptoms suggestive of hypoglycaemic events as AEs, see Section 6.4.3.10.

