6.3 Efficacy

Baseline is defined as the last non-missing value before the first dose of double-blind treatment on Week 1 (Day 1).

Self-monitoring of plasma glucose should be done in order to reduce the risk of prolonged periods of undetected hyperglycaemia or to confirm hypoglycaemia. Patients will be asked to do self-monitoring of plasma glucose using glucometers provided by AstraZeneca. The patients will receive training on the use of the glucometer, according to the manufacturer's instruction.

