12.2.2 Safety

The Safety analysis set will be used for the analysis of the safety and tolerability data.

The number and percent of patients with an AE will be summarised for each treatment group. Changes from baseline to each scheduled time point for each clinical laboratory test, vital signs and ECG will be summarised by treatment group. The number and percent of patients with a predefined marked abnormality in clinical laboratory tests will be summarised by treatment group. In addition, the incidence of hypoglycaemic events will be presented per treatment group. Hypoglycaemic events will also be summarised by major or minor incidence (see Section 6.4.11 for definitions of major and minor). The aforementioned safety analyses will be presented by relevant time point as set out in the Study Flow Chart (see Section 3.1).

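### Protocol Section 6.4.11 names the central laboratory as the source of the glucose values that define hypoglycaemia, which conflicts with the home-glucometer process in Sections 6.3, 6.4.11 and 6.5.1.1

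*Protocol*

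**What the plan says.** Section 6.4.11 sets three categories. A *major* event is symptomatic, needs outside help because of severe impairment, and comes "with plasma glucose level <3.0 mmol/L (<54 mg/dL), and prompt recovery after glucose or glucagon administration". A *minor* event is either symptomatic with plasma glucose below the same cut-off and no need for help, or asymptomatic with a blood glucose measurement below it. The third category is "Events suggestive for hypoglycaemia, with symptoms that the patient experiences as hypoglycaemia and no confirmative measurement". None of the three names a laboratory or a device.

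The next sentences do name a source: "Plasma glucose values will be obtained from the central laboratory. Therefore, the corresponding plasma glucose values will be used to define hypoglycaemia".

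The same section asks patients to self-monitor and to enter finger-stick values in the diary. For each event it collects "If finger-stick value obtained and the plasma glucose value", and it adds: "The patient diary will be reviewed and data regarding hypoglycaemic events transcribed into the eCRFs at each scheduled visit". Section 6.3 gives the purpose of home testing: "Self-monitoring of plasma glucose should be done in order to reduce the risk of prolonged periods of undetected hyperglycaemia or to confirm hypoglycaemia". Section 6.5.1.1 says that the supplied glucometer checks plasma glucose at home, and that event data go from the diary to the hypoglycaemia section of the eCRF.

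In the analysis, Section 12.2.2 presents overall incidence of hypoglycaemic events per arm, and then: "Hypoglycaemic events will also be summarised by major or minor incidence", pointing back to Section 6.4.11 for the definitions. Discontinuation criterion 3 in Section 5.8 uses the same two terms.

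**The concern.** Both major and minor require a glucose value below 3.0 mmol/L. If that value has to come from the central laboratory, an event at home can never supply it. If it may come from the glucometer, the central-laboratory sentence is wrong. The protocol supports both readings, and they give different safety tables from the same data.

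Hypoglycaemia is a central tolerability question here. All patients take a sulfonylurea, and Sections 1.1.5 and 1.4 report a numerically higher hypoglycaemia rate when saxagliptin was added to an intermediate sulfonylurea dose than with up-titrated sulfonylurea alone. Section 6.4.3.10 keeps hypoglycaemic events out of the regular adverse-event section unless they are serious, so the ordinary adverse-event tables are no backstop for the classification. If the source is left open until the data are unblinded, the rule behind this safety summary could be chosen with the results in view.

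**Working it through.** **Threshold.** Section 6.4.11 gives 3.0 mmol/L as 54 mg/dL. Check: 3.0 × 18.0 = 54.0 mg/dL. The figure reproduces, so the problem is the source of the reading and not the cut-off.

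**Where central glucose values exist.** Table 2 schedules fasting plasma glucose at Visits 3 to 9 (7 samples) and postprandial glucose at Visits 3 and 9 (2 samples). Table 4 has the same counts. Total: 7 + 2 = 9 per completer, all in clinic. The only other central glucose samples are repeats to confirm a *high* fasting value (Section 5.8, criteria 5 and 6; Section 6.5.1.1). No section arranges a central sample after a low home reading.

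**Where home values exist.** Sections 3.1 and 6.5.1.1 ask for fasting self-monitoring at least every other day: 168 / 2 = 84 readings over the treatment period. Section 6.5.1.1 also allows local practice, so 84 is an assumption and not a firm minimum. Section 5.8 mentions daily testing, which would give 168. Central values are then 9 / (9 + 84) = 9.7% of scheduled readings, or 9 / (9 + 168) = 5.1% with daily testing. These are shares of scheduled readings, not of events.

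**Classification under each reading.**

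| Episode | Central laboratory only | Glucometer value accepted |
|---|---|---|
| Home, symptomatic, finger-stick <3.0, no help needed | Suggestive at best | Minor |
| Home, asymptomatic, finger-stick <3.0 | None of the three (no symptoms, no central value) | Minor |
| Home, helped by another person, finger-stick <3.0, prompt recovery | Suggestive at best | Major |
| Home, symptomatic, not measured | Suggestive | Suggestive |
| At a visit, asymptomatic, central value <3.0 | Minor | Minor |

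The first three rows change with the reading, and all are home events. *Suggestive at best* is itself strained, because that category presumes no confirming measurement and in these rows a measurement was made.

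**Effect on counts.** To turn the table into an incidence one would need the rate of home events and the share with a finger-stick value. The protocol gives neither, so no figure can be computed.

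**The case against.** The strongest defence is that the central-laboratory sentence only explains why the cut-off is expressed as plasma rather than blood glucose. It speaks of the corresponding plasma values and then restates the threshold. The rest of the protocol runs on home readings: the purpose of self-monitoring, the diary, the eCRF fields, and the instruction in Section 6.4.11 that patients contact the investigator after a major event or more than one minor event since the last visit. That instruction works only if such events can be recognised between visits.

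This stands as evidence of likely intent. It does not remove the contradiction. On the defence's own reading, the premise that plasma values come from the central laboratory is untrue for home events, and the minor definition still uses plasma in one limb and blood in the other with the same cut-off. Sections 5.8 and 6.5.1.1 also contain a genuine central-confirmation rule for high fasting glucose, so a programmer has some reason to take the hypoglycaemia sentence at face value.

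Two further objections hold. First, a reader might infer that major and minor events will be counted at close to zero and that any difference between arms will be hidden. The documents do not support that: it follows only from the literal reading, no event rate stands behind it, low values at visits would still count, and Section 12.2.2 reports overall incidence, which includes symptomatic episodes without a measurement. Second, a reader might call it an error that an assisted episode with no glucose reading cannot be major. Requiring a glucose value is a stated definitional choice, which Section 6.4.11 attributes to the CPMP guidance. Such an episode is still recorded, with the intervention needed for recovery. It is not part of this point.

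**Conclusion.** The contradiction is real, and the text is wrong as written. One sentence of Section 6.4.11 assigns the defining glucose values to a source that does not exist for home events, while Sections 6.3 and 6.5.1.1 and the remainder of 6.4.11 assign confirmation and recording to the glucometer. Taken literally, the rule removes every home event from the major and minor rows of the Section 12.2.2 summary and leaves asymptomatic home lows outside all three categories. Under the glucometer reading nothing is lost.

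The effect is confined to the split into major and minor; overall incidence survives. Its size is unknown. The conclusion rests on the schedule in Table 2 and on the absence of any provision for a central sample after a home low. It does not depend on the 84 home readings, which assume every-other-day testing.

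**What to change.** Reconcile Sections 6.3, 6.4.11 and 6.5.1.1 before unblinding:

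- In Section 6.4.11, replace the central-laboratory sentence with a statement that, for the analysis, the recorded glucometer plasma glucose value (diary and eCRF) classifies the event, and that a central value is used only for an event occurring at a visit. Use one term, plasma glucose, in both limbs of the minor definition.
- In Section 12.2.2, summarise suggestive events alongside major and minor, so that all recorded events are accounted for.
- Discontinuation criterion 3 in Section 5.8 relies on the same categories and must be reconciled with whatever source is stated. No clinical rule is proposed here.

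The cost is a few sentences and one table row. Section 6.4.11 already collects the finger-stick and glucose information for each event, so no new data are needed.

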6.5 Patient reported outcome

6.5.1 Patient diary

Patients will be supplied with diaries at Visit 2 to Visit 8 for the 24-week double-blind treatment period. The diaries will be collected at each subsequent visit and kept in the Investigator Study File and a new diary for the next visit period will be handed over to the patient. The patient should be instructed to enter FPG values in the diary section for hypoglycaemic events (see Section 6.4.11).

6.5.1.1 Method of assessment

Glucometer measurements

Patients will be provided with a glucometer at Visit 2 to check their plasma glucose level at home. Patients will be instructed on the use of the glucometer and the recording of their FPG levels in the diary. The FPG level should be self-monitored at least every other day or according to local clinical practices for the duration of the study (Visit 2 to Visit 9).

The glucometer is equipped with a memory which should be reviewed by the study centre at each visit, from Visit 3 to Visit 9.

If self-monitored FPG is above 15 mmol/L (270 mg/dL) between Visit 3 and Visit 6, or if FPG is above 12.2 mmol/L (220 mg/dL) between Visit 6 and Visit 9, the patient is highly recommended to repeat the self-monitoring of FPG within 2 days. If this second FPG is still above 15 mmol/L (270 mg/dL) between Visit 3 and Visit 6, or above 12.2 mmol/L (220 mg/dL) between Visit 6 and Visit 9, the patient should contact the study centre and be scheduled for a FPG measurement at the study centre (analysed by the central laboratory).

Diary for hypoglycaemic events

The patient will be asked to self-monitor plasma glucose levels and symptoms suggestive of hypoglycaemia. If a hypoglycaemic event occurs, the start and stop date, time of the day, plasma glucose values, and the presence of the following symptoms: sweating, shakiness, pounding heart, hunger, confusion, dizziness/lightheadness, drowsiness, nausea and headache should be recorded in the diary. If any other symptoms occur concurrently, these should also be recorded and specified in the diary. The study centre personnel will review the diary at each following visit (Visit 3 to Visit 9) and enter data into the 'Hypoglycaemic adverse event' section in the eCRF.

